**2. Objectives (include all primary and secondary objectives)**

**Aim #1:** Determine clinical outcomes as they relate to pain control of the interscalene nerve block vs. liposomal bupivacaine injection in patients undergoing total shoulder arthroplasty.

This will be evaluated using the Visual Analog Scale (VAS) pain score and pain medication data and side effects from opioids (nausea/vomiting, GI distress, itching, etc) from inpatient medical records and through daily follow-up questionnaires after patients are discharged until 96 hours after surgery. Data will be collected at routine clinical follow up appointments after surgery.

**Aim #2:** Determine the length of stay of liposomal bupivacaine compared to interscalene nerve block in patients undergoing total shoulder arthroplasty and calculate costs associated with any differentials.

**3. Background** (briefly describe pre-clinical and clinical data, current experience with procedures, drug or device, and any other relevant information to justify the research)

We conducted a retrospective cohort analysis of 58 shoulder arthroplasties performed by a single surgeon. Patients who underwent total, reverse, and hemiarthroplasties were included. The control group included patients who received interscalene nerve blocks for postoperative pain control. The experimental group included patients who received periarticular liposomal bupivacaine injections. Baseline demographic data included age, sex, body mass index (BMI), and American Society of Anesthesiologists' (ASA) classification of physical health. We measured length of stay (LOS), pain medication administration, numeric rating scale (NRS) pain scores at four time intervals postoperatively (0.5 hours, 8-14 hours, 18-24 hours, 27-36 hours). Statistical analysis was performed.

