There were 21 patients in the IS nerve block group and 37 patients in the liposomal bupivacaine group who met all inclusion criteria. Baseline demographic data for age ( $p=0.53$ ), sex ( $p=0.71$ ), BMI ( $p=0.09$ ), and ASA ( $p=0.33$ ) did not differ between groups. The primary outcome measure, NRS pain score, showed no significant differences between groups at 0–1 hours after surgery ( $P = .99$ ) or 8–14 hours after surgery ( $P = .208$ ). At 18–24 hours after surgery, the liposomal bupivacaine group had a lower mean NRS score than the ISNB group ( $P = .001$ ). This was statistically significant when taking repeated measures of variance into account (Fig. 1). Mean NRS score was also lower for the liposomal bupivacaine group at 27–36 hours after surgery ( $P = .029$ ). This was not statistically significant when repeated measures of variance were considered (Table II).

There was no difference in the amount of intravenous acetaminophen given during the hospital stay between groups. There was no statistically significant difference in opioid consumption on postoperative day 1 in the hospital ( $P = .59$ ). However, there were significant differences between groups on postoperative days 2 and 3 (Fig. 2). On postoperative day 2, the ISNB group required significantly more opioids (112 mg) than the liposomal bupivacaine group (37 mg) ( $P = .001$ ). The ISNB group also required significantly more opioids (25 mg) on postoperative day 3 than the liposomal bupivacaine group (5 mg) ( $P = .002$ ).

Sixteen of 37 patients in the liposomal bupivacaine group and 2 of 21 in the ISNB group (Table III) were discharged on the day after surgery. The mean LOS was  $46 \pm 20$  hours for the liposomal bupivacaine group and  $57 \text{ hours} \pm 14$  hours for the ISNB group ( $P = .012$ ).

There were no major cardiac or respiratory events in either group. No long-term paresthesias or neuropathies were noted. There were no readmissions for either group.

Liposomal bupivacaine injections may provide better pain control 18-24 hours after surgery and shorten hospital stays after shoulder arthroplasty compared to interscalene nerve blocks as a means of postoperative pain control. Based on these results, larger analytic studies including randomized trials should be performed to explore the potential benefits of liposomal bupivacaine injections for pain control after shoulder arthroplasty.

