#### **4. Study Procedures**

- a. Study design, including the sequence and timing of study procedures (distinguish research procedures from those that are part of routine care).

Study Design: After the decision to proceed with shoulder replacement surgery, patients will be asked to participate in this prospective randomized clinical trial.

Study Groups:

- Group 1 will receive interscalene nerve block.
- Group 2 will receive liposomal bupivacaine with local bupivacaine for postoperative analgesia.

Study Procedures:

1. Before Surgery: The Informed Consent process will be completed prior to any data collection. Consent will be completed after explanation of each treatment group and the data to be collected. The following baseline data will be collection prior to surgery:

- Demographics (including age, sex, BMI, work status, living environment)
- Medical and Surgical History
- ASA Physical Status Classification
- Charlson Comorbidity Index Score
- Pain History and Medications
- VAS pain score

2. Randomization: Subjects will be randomized prior to surgery into one of the two perioperative analgesia groups. Randomization will be stratified by gender.

3. Surgery/Inpatient Stay:

- Group 1: Patients in the interscalene nerve block group will be given a single shot block in the preoperative area by a fellowship-trained anesthesiologist. The shot will contain a local anesthetic like 5% Ropivacaine (5 mg/1 mL) with a 44 millimeter 22 gauge needle with the patient in the supine position.
- Group 2: The surgeon at each site will be trained prior to enrollment on the correct way to perform Exparel injections intraoperatively. The surgeon will give patients in the liposomal bupivacaine group the periarticular injection

containing 266 mg of the drug in 40 mL injectable saline in the operating room; local 0.5% bupivacaine-epinephrine will also be used not to exceed dose limits.

- Surgical/Inpatient Data Collection:
  - Pre-op procedure time
  - Surgical time
  - PACU time
  - Admission/Discharge time and date
  - Estimated blood loss
  - Procedures performed
  - Inpatient pain medications administered
  - Patient VAS scores every 6 hours after surgery

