#### 4. After Discharge:

- Patients will record the following information after discharge up until 96 hours from their surgery:
  - VAS scores every 6 hours
  - Pain medication consumption (dosages, times)
  - Opioid-related side effects
  - Level of satisfaction with pain management
- Study staff may conduct reminder phone calls to ensure patients complete outpatient data collection. The outcome assessor will be blinded to the treatment group.
- Patients will record their VAS pain scores again at their 1st postop appointment, which typically occurs 10-18 days after surgery.

Sample Size: There will be 60 patients in each group, for a total study population of n = 120.

Study Locations: This will be a multi-center study. The sample size will enroll 120 (to account for 15% drop out rate) patients total, with approximately 30 patients enrolled at each site. The other participating sites are as follows:

[name]  
Sports Medicine and Shoulder Service  
University of Texas, Southwestern Medical Center  
[name]  
[name]

[name]  
MedStar St. Mary's Hospital  
[name]  
[name]

[name]  
William Beaumont Army Medical Center  
[name]  
[name]

**Aim #2:** Determine the length of stay of liposomal bupivacaine compared to interscalene nerve block in patients undergoing total shoulder arthroplasty and calculate costs associated with any differentials.

- b. Study duration and number of study visits required of research participants.

Patients will be enrolled in this study for 2 weeks after their surgical date. This time frame will include their hospital stay and include their time at home after discharge up until 96 hours after their surgery, and their 2-week postop appointment data. If patients are not scheduled for their postop appointment within 10-18 days after surgery (which is standard clinical practice), the study team will call the patient to obtain their pain score and medication data. Patient names will be stored in a password-protected database for 30 days after discharge to calculate 30-day readmission rates.

Routine patient follow up is typically at 3, 6, and 12 months for the first year. Pain data and patient reported outcomes are collected at these visits as routine clinical care. Patients routinely complete the ASES and EQ-5D questionnaires at their 12 month follow up appointment.

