## 7. Study Statistics

- a. Primary outcome variable.

- VAS pain score at 24 hours postop.

- b. Secondary outcome variables.

- VAS scores at all other data points,

- Pain medication consumption (narcotics, NSAIDs, Tylenol)
- Opioid-induced side effects (nausea, vomiting, constipation)
- Length of hospital stay
- 30 day readmission rate.

- c. Statistical plan including sample size justification and interim data analysis.

A power analysis was performed to determine the sample size needed to determine noninferiority between groups with respect to VAS pain score. The minimal clinically important difference of VAS is 1.4 cm^13. The number was found to be 42 patients in each group, for a total n = 84. To ensure we reach this number, each of the 4 sites will aim to enroll 30 patients, to account for drop out.

The age of the two treatment groups will be compared using t-test. Sex distribution and the ASA scores of the groups will be compared using a chi-squared test and a Fisher exact test, respectively.

The median and interquartile range of the VAS scores at each of the time points measured will be tabulated by treatment group, and at each time point the difference between groups will be tested using non-parametric rank sum tests.

We will test the longitudinal trajectory of VAS scores over time, taking into account repeated measurements in the same patients using linear mixed model analysis. Treatment group, time period as a categorical variable, and the interaction between treatment and time period will be included as fixed effects, and patient ID will be included as the random effect. An initial omnibus test will be performed for all treatment and treatment by time interaction effects. If significant, the treatment by time interaction will be tested subsequently for each of the measurement periods.

The association of day of discharge (as a categorical variable) with treatment will be tested using the Fisher exact test.

- d. Early stopping rules.

We will monitor operative and post-operative complications including implant failures, nerve injuries, hematomas, and infections. We do not anticipate issues with these complications, as both techniques are in routine use in our current clinical practice. We did not find any differences in the complication rates in our retrospective cohort analysis.

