## **9. Benefits**

- a. Description of the probable benefits for the participant and for society.

There is no direct benefit to the participant in the study. This study could help determine if one pain control technique is superior to the other. This could result in higher quality care for patients who undergo total shoulder arthroplasty in the future. It could result in savings for the healthcare system if one technique is found to be cost-effective.

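### Aim 2 needs a length-of-stay difference that can be costed, but the only stated analysis is an unordered Fisher test on discharge day

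*Combined protocol and SAP*

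**What the plan says.** Aim 2 appears in section 2 (Objectives) and again in section 4 (Study Procedures), after the list of sites: "Determine the length of stay of liposomal bupivacaine compared to interscalene nerve block in patients undergoing total shoulder arthroplasty", and then "calculate costs associated with any differentials". Section 7b (secondary outcome variables) lists "Length of hospital stay" without a unit or summary measure. Section 7c (statistical plan) gives one sentence of analysis: "The association of day of discharge (as a categorical variable) with treatment will be tested using the Fisher exact test".

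The inpatient data list in section 4 includes "Admission/Discharge time and date", so stay in hours can be computed for each patient. Section 3 (Background) reports the retrospective cohort in two ways. One is discharge on the day after surgery ("Sixteen of 37 patients in the liposomal bupivacaine group and 2 of 21 in the ISNB group"). The other is mean stay: 46 ± 20 h with liposomal bupivacaine and 57 ± 14 h with the interscalene block.

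Section 9 (Benefits) holds out a cost result: "It could result in savings for the healthcare system if one technique is found to be cost-effective". No section states how a cost difference would be calculated.

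**The concern.** A cost for a difference in stay needs the size and direction of that difference, in hours or days, with its uncertainty. A Fisher exact test on discharge day as a category gives a p-value for whether the two distributions are the same. It treats days 1, 2 and 3 as labels with no order, and the plan attaches no estimate to it.

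One of the trial's two aims therefore has no matching estimate in the plan. Mean or median, hours or nights, and the route to a cost would be chosen after the data are seen. The retrospective cohort reported both discharge counts and mean hours, but the trial plan states an analysis only of discharge day.

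**Working it through.** **Inputs.** Retrospective stay: 46 ± 20 h (n = 37) and 57 ± 14 h (n = 21), section 3. Next-day discharge: 16/37 and 2/21, section 3. Trial size: 60 per arm enrolled and 15% drop-out (section 4); 42 per arm required (section 7c). 60 × 0.85 = 51 per arm is shown as a middle case, although drop-out may not apply to a stay recorded in hospital.

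**1. The cohort's own figures.** The difference is 57 − 46 = 11 h.
- SE = √(20²/37 + 14²/21) = √(10.81 + 9.33) = 4.49 h, Welch df 53.4.
- 95% CI: 11 ± 9.0, about 2 to 20 h; Welch p = 0.018, pooled p = 0.030.
- The document gives P = .012. The rounded summaries do not reproduce it, but the test is not named and nothing here depends on it.
- Fisher on 16/37 v 2/21 gives p = 0.0085. That figure contains no hours or days; the 11 h comes only from the mean analysis.

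**2. What the Fisher test ignores (constructed counts, illustration only).**

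| Per arm | Days 1/2/3, arm A v arm B | Fisher p | Difference in mean (95% CI, Welch) |
|---|---|---|---|
| 60 | 16/28/16 v 7/46/7 | 0.0031 | 0 h (−5.4 to 5.4) |
| 51 | 14/23/14 v 6/39/6 | 0.0055 | 0 h |
| 51 | 22/22/7 v 9/27/15 | 0.012 | 9.9 h (3.4 to 16.4) |

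Days are converted at 24 h. In row 3 the means are 87/51 = 1.71 and 108/51 = 2.12 days, and 21/51 × 24 = 9.9 h. In row 1 the rank-sum test, which uses the order, gives p = 1.0.

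Relabelling shows the same thing. Take days 1 to 4 with counts 20/20/15/5 v 8/22/20/10 at 60 per arm. The mean difference is (125 − 152)/60 = −0.45 days. With the day labels reversed it is (175 − 148)/60 = +0.45 days, and the Fisher p-value does not change. The p-value therefore fixes neither size nor direction.

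**3. What a mean difference would deliver.** Half-width = t(0.975, Welch df) × √((20² + 14²)/n), assuming the cohort SDs carry over.

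| n per arm | SE (h) | df | Half-width (h) |
|---|---|---|---|
| 60 | 3.15 | 105.6 | 6.2 |
| 51 | 3.42 | 89.5 | 6.8 |
| 42 | 3.77 | 73.4 | 7.5 |

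At 60 per arm the half-width is 5.1 h if both SDs are 14 h and 7.2 h if both are 20 h.

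**4. Power is not the issue.** At the cohort's rates, Fisher on next-day discharge alone has about 94% power at 42 per arm and 99% at 60. A two-sided 5% test of an 11 h mean difference, on the same SDs, has about 83% and 94%.

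**The case against.** The strongest reply is that little is wrong. Length of stay is one of several secondary outcomes, the named test is valid, and the times are collected. Nothing in the text bars reporting the discharge-day table or stay in hours, as the cohort report did. The equal-mean counts were built so that the means cancel, whereas the cohort shows a shift towards earlier discharge, and under a shift the Fisher test and the mean difference point the same way (row 3 of the first table). A Welch mean is also only one choice among several: it is sensitive to long stays and does not account for the four sites. Stay multiplied by a unit cost would cover only part of the cost the abstract has in mind, which includes giving the block.

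Most of this stands, and it sets the limits of the point. A reader might infer that the Fisher test is invalid or inflates type I error. It does not: rejecting when discharge-day distributions differ is a correct rejection. A reader might also infer that this trial is likely to produce a significant result with no difference in mean stay. The documents give no support for that. Nor is a stay difference unobtainable. What survives is that the stated analysis does not name the quantity that Aim 2 has to cost, although the data for it will be in hand.

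**Conclusion.** The point holds as a mismatch between a stated aim and its stated analysis. Section 7c specifies no length-of-stay difference and no interval, and the one test it names ignores the order of the days. The loss is in pre-specification. The primary outcome (VAS at 24 hours), type I error and data collection are unaffected, and no loss of power is claimed.

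The missing result would be informative: an interval of roughly ±6 to ±7.5 h around the difference, set against 11 h in the retrospective cohort. Those widths rest on the cohort's SDs applying to the trial. The mismatch itself follows from the text and needs no such assumption. It should be corrected, but it does not threaten the trial's main conclusion.

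**What to change.** In section 7c, add the following to the Fisher sentence:

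1. The main Aim 2 analysis is the between-arm difference in mean length of stay, in hours, from the recorded admission and discharge times, with a 95% confidence interval (for example Welch).
2. Discharge day is tabulated by arm, with an ordered test (rank-sum or trend) in support. The Fisher test is optional.
3. The bed-stay part of the cost difference is obtained by applying a stated unit cost, with its source, to this difference and to both confidence limits. The text should say that it excludes block, drug and procedure-time costs, so that it is not read as a full cost-effectiveness result.

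The cost is a few sentences and one unit cost to be named, with no new patient data and no change in sample size. There are two downsides. A mean can be pulled by a few very long stays, so the discharge-day table should be shown beside it. A fixed unit cost carries the uncertainty in stay but not in price.

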## 8. Risks

- Medical risks, listing all procedures, their major and minor risks and expected frequency.
- Steps taken to minimize the risks.
- Plan for reporting unanticipated problems or study deviations.
- Legal risks such as the risks that would be associated with breach of confidentiality.
- Financial risks to the participants.

No additional risk associated with study for the participant, as study procedures are standard clinical care. There is a remote risk to the study subjects if there is a breach in confidentiality. All data will be collected and entered into a REDCap database. Data will be extracted from REDCap at the time of analysis.

To manage this, we will incorporate the following standard procedures:

- 1) Patient identifiers key to database will be kept on each site in password protected excel document.
- 2) We will maintain the data in accordance with University and IRB standards. Data will be kept on password protected university servers, and any printed material will be kept in a locked file cabinet.
- 3) Only investigators associated with the study will have access to the data

The reporting of unanticipated problems or study deviations will be reported to the JHM IRB pursuant to Hopkins IRB policies.

## **9. Benefits**

- a. Description of the probable benefits for the participant and for society.

There is no direct benefit to the participant in the study. This study could help determine if one pain control technique is superior to the other. This could result in higher quality care for patients who undergo total shoulder arthroplasty in the future. It could result in savings for the healthcare system if one technique is found to be cost-effective.

## **10. Payment and Remuneration**

- a. Detail compensation for participants including possible total compensation, proposed bonus, and any proposed reductions or penalties for not completing the protocol.

Patients will not be compensated for their participation in this study.

## **11. Costs**

- a. Detail costs of study procedure(s) or drug (s) or substance(s) to participants and identify who will pay for them.

The costs of study procedures will be covered by the participant's health insurance because these procedures are both used for routine care.

